### **3. STUDY DESIGN**

#### **3.1. Scientific rationale for study design**

As the rMenB+OMV NZ licensure in the US was issued through accelerated approval, the FDA has requested to demonstrate the effectiveness of the vaccine against an extended panel of serogroup B meningococcal strains (MenB) as a post-marketing commitment in US adolescents and young adults, thus confirming that the vaccine can protect against diverse meningococcal B strains prevalent in the United States.

The availability of a pentavalent meningococcal vaccine in a single administration would however reduce the number of injections and could increase coverage for meningococcal disease caused by *N. meningitidis* serogroups A, B, C, W, and Y worldwide. GSK's investigational MenABCWY combination vaccine is intended to protect against 5 of the most prevalent serogroups of *Neisseria meningitidis* (A, B, C, W, Y) in humans.

Hence, along with the licensed MenB vaccine (*Bexsero*), this Phase III study will also assess the safety, effectiveness, and immunogenicity of the investigational MenABCWY vaccine.

##### Rationale for effectiveness assessment

As mentioned above, one of the primary purposes of this study is to evaluate the effectiveness of 2 or 3 doses of rMenB+OMV NZ and of 2 doses of the MenABCWY vaccines in healthy adolescents and young adults by measuring the bactericidal activity against 110 endemic US *N. meningitidis* serogroup B strains using an endogenous complement human Serum Bactericidal Assay (enc-hSBA). Sera from the ACWY group receiving the MenACWY vaccine will also be tested against serogroup B meningococcal strains by enc-hSBA as a control for test-based effectiveness assessment. The overall vaccine effectiveness (VE) against all 110 strains combined will be computed by means of a generalised linear model. For additional details see statistical analysis section of the Clinical Study Protocol (Protocol Section 10).

##### Rationale for lot-to-lot consistency assessment

MenABCWY is a reconstituted vaccine with the lyophilised 'ACWY component' and liquid\_rMenB+OMV NZ. The MenB component has the same formulation as the commercial *Bexsero*. To demonstrate that the lots of the investigational MenABCWY vaccine are adequately representative of the formulation intended for marketing, equivalence will be assessed for 3 different lots of the ACWY component of the ABCWY vaccine.

Rationale for non-inferiority assessment of MenABCWY vs MenACWY and rMenB+OMV NZ

The study aims to also demonstrate that the investigational combination MenABCWY vaccine is not inferior to a licensed MenACWY vaccine (*Menveo*) and a licensed MenB vaccine (*Bexsero*) which are part of the current standards of care in the US for prevention of invasive disease caused by *N. meningitidis* serogroups A, C, W, Y and by *N. meningitidis* serogroup B, respectively.

Rationale for blood volume collected:

In order to provide the necessary serum volume for the bactericidal assays (enc-hSBA and/ or hSBA(s)), 25 mL whole blood will be collected at Visit 2, Visit 4 and Visit 6. At pre-vaccination (Visit 1), 20 mL whole blood will be collected to provide the necessary serum volume for the hSBA.

Blood samples are taken from all subjects irrespective of the testing status in order to maintain the study blind. Refer to Protocol Section 8.4.2.1 for further details.

Rationale for the selected vaccination schedules

rMenB+OMV NZ: This study aims at demonstrating the VE of the rMenB+OMV NZ vaccine administered as 2-dose vaccine, either with a shorter interval (0,2-months) or a prolonged interval (0,6-months) between doses. A 3-dose schedule has been also added to better characterise the VE.

Note: The rMenB+OMV NZ in the ACWY group is administered in a 0,1-months schedule. This interval is within the recommendations in the summary of product characteristics of *Bexsero* and helps in maintaining the blind. No objectives are associated with this schedule of rMenB+OMV NZ.

MenABCWY: A number of different vaccine formulations were evaluated in MenABCWY Phase I and II clinical studies. The formulation with the same active ingredient composition as the rMenB+OMV NZ (*Bexsero*) and MenACWY (*Menveo*) vaccines was chosen as the final formulation of the investigational MenABCWY vaccine. Two doses administered 6 months apart (0,6-months) is considered the optimal dosing schedule, based on serogroup B immunogenicity results from MenABCWY Phase II clinical studies.

[figure not shown]
MenACWY: As a comparator for serogroup A, C, W, and Y vaccine effectiveness and immune responses, a single dose of MenACWY vaccine is administered to subjects in the ACWY group. To conform with the standard of care (also in alignment with current ACIP routine immunisation recommendations in US), subjects in the MenB\_0\_2\_6 and MenB\_0\_6 groups will also receive a dose of MenACWY at Day 211 and Day 61, respectively.

### 3.1.1. Rationale for the use of placebo

For this study, a placebo (saline solution) will be administered as presented in Figure 1. A placebo is the only available option to minimize possible introduction of reporting bias in collecting information about AEs and to ensure the same number of vaccinations are administered to subjects assigned to either of the six study groups.

### 3.2. Overall design

**Figure 1** Study design overview

N = number of subjects; d = dose; V = visit; D = day; T=Telephone call

Refer to Protocol Table 3 for details on all visits

Note: Home visits may be performed only by sites authorised (as per local regulations and sponsor agreement), with approved site level standard operating procedures (SOP) provided that the compliance with protocol procedures are ensured.

Protocol waivers or exemptions are not allowed unless necessary for the management of immediate safety concerns. Therefore, adherence to the study design requirements, including those specified in the schedule of activities (Protocol Section 2), are essential and required for study conduct.

- Type of study: self-contained

- Experimental design: This is a phase III, randomised, controlled, observer-blind, multi-center study to evaluate effectiveness, immunogenicity and safety of rMenB+OMV NZ and MenACWY vaccines. A total of 3651 healthy adolescents and young adults aged 10-25 years will be enrolled and randomised (5:5:3:3:3:1 ratio) to one of the six parallel study groups:
  - **MenB\_0\_2\_6 group**\*: subjects will receive 3 doses of rMenB+OMV NZ at Day 1, Day 61 and Day 181 (0, 2 and 0,2,6-months schedule). These subjects will receive 1 dose of the MenACWY vaccine at Day 211\*\*.
  - **MenB\_0\_6 group**: subjects will receive 2 doses of rMenB+OMV NZ at Day 1 and Day 181 and 1 dose of MenACWY vaccine at Day 61 (rMenB+OMV NZ, 0,6-months schedule). These subjects will receive 1 dose of placebo at Day 211\*\*.
  - **ABCWY-1**: subjects will receive 2 doses of MenACWY vaccine 6 months apart (0,6-months schedule), at Day 1 and 181 with Lot 1 of the MenACWY lyophilised vial component of the vaccine. They will receive 1 dose of placebo at Day 61 and at Day 211\*\*.
  - **ABCWY-2**: subjects will receive 2 doses of MenACWY vaccine 6 months apart (0,6-months schedule), at Day 1 and 181 with Lot 2 of the MenACWY lyophilised vial component of the vaccine. They will receive 1 dose of placebo at Day 61 and at Day 211\*\*.
  - **ABCWY-3**: subjects will receive 2 doses of MenACWY vaccine 6 months apart (0,6-months schedule), at Day 1 and 181 with Lot 3 of the MenACWY lyophilised vial component of the vaccine. They will receive 1 dose of placebo at Day 61 and at Day 211\*\*.
  - **ACWY group**: subjects will receive 1 dose of MenACWY vaccine at Day 1, 1 dose of placebo at Day 61 and 2 doses of rMenB+OMV NZ at Day 181 and Day 211\*\*.

\* MenB\_0\_2\_6 group will also be evaluated for objectives pertaining to 0,2-months vaccination schedule.

Note 1: A MenB lot will be used for the pre-filled syringe component of the MenACWY vaccine.

Note 2: The groups ABCWY-1, ABCWY-2, ABCWY-3 will be pooled into a single group, ABCWY (pooled lots) (except for analysis of lot to lot consistency).

\*\* Note 3: In order to let the subjects in MenB\_0\_2\_6 group receive a dose of MenACWY vaccine and for subjects in ACWY group to receive the second dose of rMenB+OMV NZ in line with the vaccine as standard of care (also in line with the Advisory Committee on Immunization Practices (ACIP) recommendations in the US [ACIP, 2011]), the subjects in these groups will receive a vaccination of MenACWY and rMenB+OMV NZ vaccines, respectively, on Day 211 (Visit 6) after completion of the post-vaccination 3 blood sampling. To maintain the blinding of the study, subjects in the rest of the groups (MenB\_0\_6, ABCWY-1, ABCWY-2 and ABCWY-3) will receive a dose of Placebo. All these vaccines/ product administered at Day 211 are not associated with any study objectives/ endpoints (Safety assessment

conducted after 1 dose of rMenB+OMV NZ in the ACWY group at Day 181 is to maintain the blind of the study).

- Duration of the study: The study duration is approximately 18 months for each subject.
- Primary completion Date (PCD): T10; Day 541.

Refer to Glossary of terms for the definition of PCD.

- End of Study (EoS): the date of release of the last testing results, to be achieved not later than 8 months after Last Subject Last Visit (LSLV) (LSLV = T10; Day 541). If the completion of testing occurs prior the completion of the LSLV the latter date defines the end of study visit.

Refer to Glossary of terms for the definition of EoS.

- Study groups:

**Table 2 Study groups and treatment foreseen in the study**

Study Groups	Number of subjects	Age (Min-Max)	Treatment name	Vaccine/Product name
MenB_0_2_6	912	10 – 25 y	Bexsero (Injection)	rMenB+OMV NZ
			Menveo (Injection)	MenACWY
MenB_0_6	912		Bexsero (Injection)	rMenB+OMV NZ
			Menveo (Injection)	MenACWY
			Placebo (Injection)	NaCl
ABCWY-1	548		MenABCWY (with Lot 1 of ACWY) (Injection)	MenABCWY-1
			Placebo (Injection)	NaCl
ABCWY-2	548		MenABCWY (with Lot 2 of ACWY) (Injection)	MenABCWY-2
			Placebo (Injection)	NaCl
ABCWY-3	548		MenABCWY (with Lot 3 of ACWY) (Injection)	MenABCWY-3
			Placebo (Injection)	NaCl
ACWY	183		Menveo (Injection)	MenACWY
			Placebo (Injection)	NaCl
			Bexsero (Injection)	rMenB+OMV NZ

## CONFIDENTIAL

205416 [MENB REC 2ND GEN-038 (V72\_72)]  
Statistical Analysis Plan Amendment 4**Table 3 Overview of study design: Vaccination and Blood Draw Schedule**

Visits Study Day	Visit 1 Day 1	Visit 2 Day 31	Visit 3 Day 61	Visit 4 Day 91	Visit 5 Day 181	Visit 6 Day 211
Group MenB_0_2_6 N=912	Pre-vacc Blood sample  rMenB+OMV NZ	Post-vacc 1 Blood sample	rMenB+OMV NZ	Post-vacc 2 Blood sample	rMenB+OMV NZ	Post-vacc 3 Blood sample  MenACWY
Group MenB_0_6 N=912	Pre-vacc Blood sample  rMenB+OMV NZ	Post-vacc 1 Blood sample	MenACWY	Post-vacc 2 Blood sample	rMenB+OMV NZ	Post-vacc 3 Blood sample  Placebo
Group ABCWY-1 N=548	Pre-vacc Blood sample  MenABCWY-1	Post-vacc 1 Blood sample	Placebo	Post-vacc 2 Blood sample	MenABCWY-1	Post-vacc 3 Blood sample  Placebo
Group ABCWY-2 N=548	Pre-vacc Blood sample  MenABCWY-2	Post-vacc 1 Blood sample	Placebo	Post-vacc 2 Blood sample	MenABCWY-2	Post-vacc 3 Blood sample  Placebo
Group ABCWY-3 N=548	Pre-vacc Blood sample  MenABCWY-3	Post-vacc 1 Blood sample	Placebo	Post-vacc 2 Blood sample	MenABCWY-3	Post-vacc 3 Blood sample  Placebo
Group ACWY N=150	Pre-vacc Blood sample  MenACWY	Post-vacc 1 Blood sample	Placebo	Post-vacc 2 Blood sample	rMenB+OMV NZ	Post-vacc 3 Blood sample  rMenB+OMV NZ

N = number of subjects; Pre-vacc = pre-vaccination; Post-vacc = post-vaccination

- Treatment allocation: At Day 1, prior to the study vaccination, subjects will be randomised to 1 of the 6 study groups according to a 5:5:3:3:3:1 ratio.
- Blinding: Observer-blind. Kindly refer to Protocol Section 7.3 for details on blinding and unblinding procedures.
- Sampling schedule:
  - A total of 4 blood samples\* will be collected from each subject at Day 1 (pre-vaccination blood sample; approximately 20 mL), at Day 31 (post-vaccination 1 blood sample; approximately 25 mL), at Day 91 (post-vaccination 2 blood sample; approximately 25 mL) and at Day 211 (post-vaccination-3 blood sample; approximately 25 mL).
  - Urine sampling: Urine samples for pregnancy testing will be collected from female subjects of child-bearing potential at Visit 1 (Day 1), Visit 3 (Day 61), Visit 5 (Day 181) and Visit 6 (Day 211) prior to the vaccination.

\* Insufficient blood volume may lead to test cancellation and jeopardise the statistical power. Hence, every effort must be done to collect blood volume as per protocol requirements.

- Data collection: standardised Electronic Case Report Form (eCRF). Solicited symptoms will be collected using a subject Diary (electronic Diary [eDiary]).
- Safety monitoring: Regular safety follow-up will be done through telephone calls (T). There will also be an extended safety follow-up (ESFU) phone call 12 months post-vaccination 3 (Day 181; Visit 5). This ESFU phone call will also mark the study conclusion. Refer to Protocol Table 3 and Protocol Section 8.5.3 for details on the safety follow-up.

### **3.3. Number of subjects**

A total of 3651 subjects will be randomised in a ratio of 5:5:3:3:3:1; 912 each in MenB\_0\_2\_6 and MenB\_0\_6 groups, 548 in each ABCWY groups and 183 in ACWY group. Assuming a 25% drop out rate, this should provide approximately 684 evaluable subjects in each of the MenB groups, 411 evaluable subjects in each of the ABCWY groups and 137 evaluable subjects in the ACWY group.

Refer to Protocol Section 10.1 for a detailed description of the criteria used in the determination of sample size.

Withdrawals will not be replaced.

### **3.4. Subject and study completion**

A subject is considered to have completed the study, if the subject is available for the concluding contact (T10; Day 541) as described in the protocol.

Global completion of the study is required in order to provide enough subjects as defined in Protocol Section 10.1 Sample Size Determination.

## **4. ANALYSIS SETS**

### **4.1. Definition**

For purposes of analysis, the following analysis sets are defined:

#### **4.1.1. Enrolled Set**

Subject/ Subject for whom parent(s)/LAR's agreed to participate in a clinical study after completion of the informed consent process, who meet screening/eligibility criteria and randomized and/or received study intervention or undergone an invasive procedure.

#### **4.1.2. Exposed Set**

All subjects who received at least 1 dose of the study treatment. The allocation in a group is done in function of all administered treatments.

#### **4.1.3. Full Analysis Set**

All subjects who received at least 1 dose of the study treatment and have post-vaccination effectiveness or immunogenicity data.

#### **4.1.4. Per Protocol Set**

All subjects in the Full Analysis Set minus subjects with protocol deviations that lead to exclusion from the Per Protocol Set.

#### **4.1.5. Solicited Safety Set**

All subjects who received at least 1 dose of the study treatment (Exposed Set) who have solicited safety data beyond 30 minutes post vaccination.

#### **4.1.6. Unsolicited Safety Set**

All subjects who received at least 1 dose of the study treatment (Exposed Set) that report unsolicited AEs/report not having unsolicited AEs.

#### **4.1.7. Overall Safety Set**

All subjects that belong to the Unsolicited safety or/and to the Solicited safety set.

### **4.2. Criteria for eliminating data from Analysis Sets**

Elimination codes are used to identify subjects to be eliminated from analysis. Detail is provided below for each set.

#### 4.2.1. Elimination from Exposed Set (ES)

Code 1030 (Study vaccine not administered at all), 800 (Fraudulent data) and code 900 (invalid informed consent or fraudulent data) will be used for identifying subjects eliminated from ES

#### 4.2.2. Elimination from Per protocol Set (PPS)

##### 4.2.2.1. Excluded subjects

A subject will be excluded from the PPS analysis under the following conditions

**Table 4 Elimination code and condition to exclude a subject from the PPS analysis**

Code	Condition under which the code is used	Visit (timepoints) where the code is applicable	Applicable for analysis set
800	Fraudulent data	All	All
900	Invalid informed consent	All	All
1030	Study vaccine not administered at all	All	All
1050	Randomization failure	Visit 1, 3, 5	All
1060	Randomization code was broken	All	All
1070.1	Subjects got vaccinated with the correct vaccine but containing a lower volume	Visit 1, 3, 5	All
1070.2	Vaccination not according to protocol	Visit 1, 3, 5	All
1080	Vaccine temperature deviation	Visit 1, 3, 5	All
1090	Expired vaccine administered	Visit 1, 3, 5	All
1500.1	Other deviation from study procedures not able to classified under any other categories	All	All
1500.2	Any other GCP non-compliance not able to classified under any other categories	All	All
2010	Protocol violation (inclusion/exclusion criteria)	All	All
2040	Administration of any medication forbidden by the protocol	Visit 1, 3, 5	All
2050	Not withdrawn after developing withdrawal criteria other than prohibited concomitant vaccination/medication (medical condition forbidden)	All	All
2060	Concomitant infection related to the vaccine which may influence immune response (only meningococcal infection)	All	All
2080	Subjects did not comply with vaccination schedule	Visit 3, 5	All

Code	Condition under which the code is used	Visit (timepoints) where the code is applicable	Applicable for analysis set
2090	Subjects did not comply with blood sample schedule	Visit 2, 4, 6	All
2100	Serological results not available post-vaccination for all tests	Visit 2, 4, 6	All
2120	Obvious incoherence or abnormality or error in data related to testing	Visit 2, 4, 6	All
2130	Biological sample specimen procedures not compliant with protocol	Visit 2, 4, 6	All

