
Vaccine effectiveness (Test-based): MenABCWY vaccine
 
To demonstrate the effectiveness of the MenABCWY vaccine against a randomly selected panel of endemic US N. meningitidis serogroup B invasive disease strains as measured by enc-hSBA at 1 month after the last MenABCWY vaccination (0,6-months) when compared to 1 month after the MenACWY vaccination.
 
Criterion:
 
LL of the two-sided 97.5% CIΔ for vaccine effectiveness is above 65% against a randomly selected strain panel between the ABCWY group (pooled lots) and the ACWY group.
	
The percentages of samples without bactericidal serum activity using enc-hSBA against each of the endemic US N. meningitidis serogroup B strains, at 1 month after the:
 
 
last vaccination for the ABCWY group (pooled) (Day 211, Month 7), and
 
1 month after the MenACWY vaccination in the ACWY group (Day 31, Month 1).
 

Effectiveness non-inferiority: MenABCWY vaccine vs. rMenB+OMV NZ vaccine
 
To demonstrate the non-inferiority of the effectiveness of the MenABCWY vaccine (0,6-months schedule) compared to the rMenB+OMV NZ vaccine (0,2,6-months or 0,6-months or 0,2-months)† in terms of percentage of samples with bactericidal serum activity using enc-hSBA against a randomly selected panel of endemic US N. meningitidis serogroup B invasive disease strains.
 
Criterion:
 
LL of the two-sided 97.5% CIΔ for the difference in percentages of samples with bactericidal serum activity using enc-hSBA against a randomly selected panel of
	
The percentages of samples with bactericidal serum activity using enc-hSBA against each of the endemic US N. meningitidis serogroup B strains at 1 month after the:
 
 
last MenABCWY vaccination (Day 211, Month 7) for the ABCWY group (pooled lots), and
 
3-dose vaccination series of rMenB+OMV vaccine (Day 211, Month 7 in MenB_0_2_6 group) or 2-dose vaccination series (Day 211, Month 7 in MenB_0_6 group) or 2-dose vaccination series (Day 91, Month 3 in MenB_0_2_6 group)†
 

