#### **5.3.1.1. Vaccine effectiveness (Test-based): rMenB+OMV NZ - 3 doses (0,2,6-months schedule)**

Analysis set: Per-protocol set (PPS) will be the primary analysis population

Statistical method: The VE is defined as  $1 - RR = (1 - \text{percentage of samples without bactericidal serum activity at 1:4 dilution in MenB group} / \text{percentage of samples without bactericidal serum activity at 1:4 dilution in the ACWY group}) \times 100\%$  and it will be analyzed using a generalised linear model with vaccine group, strain, and randomization factors (i.e. region (US/ex-US), age category (10-17 YoA/18-25 YoA), previous MenACWY vaccination (y/n)) as independent variables. Furthermore, a repeated statement will be used to estimate the variance of the RR including correlation within subject's responses to different strains. If the statistical model does not converge due to (one of) the factor(s), a model without this/these factor(s) will be fitted instead. The response variable of the model will be the Bernoulli distributed outcome without bactericidal activity at a 1:4 dilution (i.e. response is 1 if titre  $< 4$ , and 0 if titre  $\geq 4$ ), at 1 month after the last vaccination (Month 7) in the MenB group and at Month 1 for the ACWY group. Each subject will contribute with approximately 35 measures to this analysis, each of the measures corresponding to the response variable to one of the 35 strains randomly assigned to be tested with the samples available for that specific subject.

In order to obtain the VE measure which is a measure based on the relative risk (RR), a generalised linear model will be used with the Binary distribution and link function log in order to compute the log RR and the corresponding 97.5% CI. The obtained values will be exponentiated to obtain the RR and the corresponding 97.5% CI. The VE will be computed as  $100\% \times (1 - RR)$ . Effectiveness of rMenB+OMV NZ (0,2,6-months schedule) will be demonstrated if the lower limit of the two-sided 97.5% CI for VE between MenB and the ACWY group is above 65%.

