**5.3.1.5. Vaccine effectiveness (Test-based): rMenB+OMV NZ - 2 doses (0,2-months schedule)**

See Section 5.3.1.1

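### In SAP Amendment 4, a single per-protocol set drops valid Day 31 and Day 91 results because of vaccination deviations that happen after the sample was taken

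*SAP*

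**What the plan says.** The text is that of SAP Amendment 4. Section 4 of Amendment 5 lies in a part that is not shown.

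- Section 4.1.4 defines one PPS without a timepoint: "All subjects in the Full Analysis Set minus subjects with protocol deviations that lead to exclusion from the Per Protocol Set".
- Section 4.2.2.1 makes the subject the unit of exclusion: "A subject will be excluded from the PPS analysis under the following conditions".
- Table 4 lists vaccination-type codes 1050, 1070.1, 1070.2, 1080, 1090 and 2040 at Visits 1, 3 and 5. Code 2080, "Subjects did not comply with vaccination schedule", is listed at Visits 3 and 5. The sample codes 2090 ("Subjects did not comply with blood sample schedule"), 2100, 2120 and 2130 are listed at Visits 2, 4 and 6. Every row has *All* as the applicable analysis set.
- Section 5.3.1.1, on test-based VE, states that "Per-protocol set (PPS) will be the primary analysis population". The outcome is read "at 1 month after the last vaccination (Month 7) in the MenB group and at Month 1 for the ACWY group". Section 5.3.1.9 applies the same method to MenABCWY.
- Section 5.3.1.5, the 0,2-months VE, says only "See Section 5.3.1.1", so it inherits the PPS. Section 5.3.2.5 places its outcome one month after the second dose, which is Day 91.
- Section 5.3.1.8, on 4-fold-rise non-inferiority against MenACWY, uses the PPS restricted to subjects without previous ACWY vaccination. Table 1 reads the ACWY arm at Day 31.

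**The concern.** A per-protocol set should drop a subject when a deviation could have spoiled the result being analysed. A Day 61 or Day 181 vaccination deviation cannot alter a serum drawn at Day 31, and a Day 181 deviation cannot alter one drawn at Day 91. Under the rule as written, each of these still removes the subject from the primary analysis of the earlier sample.

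Two things are at stake. One is precision: the ACWY arm is the smallest (183 randomised). It is the denominator of the overall test-based VE and the comparator for the ACWY non-inferiority objective. The other is that the early results become conditional on what subjects did after the outcome was fixed. A further issue is reproducibility. The sample codes can be read in two ways, so two programmers could build different primary populations from the same table.

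**Working it through.** **The plan's own numbers (Section 3.3).** With 25% dropout: 912 × 0.75 = 684; 548 × 0.75 = 411; 183 × 0.75 = 137.25, stated as 137. The groups sum to 2 × 912 + 3 × 548 + 183 = 3651. All of these reproduce. None of them measures late deviations.

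**What the visit column means.** The column might be thought to mean elimination by timepoint. Table 3 rules this out for the vaccination-type codes. Visits 3 and 5 have no blood draw, and Visit 1 has only the pre-vaccination sample. For these codes the column can only say where the deviation occurred. The column that could say which analysis is affected reads *All*.

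The July 2019 SAP used the same layout but filled in that last column. It defined separate Month 3 and Month 7 PPS, and the Month 3 set counted only deviations before Month 3. Its Table 4 sent Day 181 deviations under codes 1070, 1080, 1090 and 2080 to Month 7 only, and split the sample codes by visit. Amendments 1 to 4 carry *All* throughout, although a Month 1 reading had by then been added.

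For the sample codes the argument from Table 3 does not apply. Visits 2, 4 and 6 are exactly the post-vaccination sampling visits, so both readings are open.

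**Size, as an illustration.** Assumption: an independent excluding deviation with probability r at each later visit, for r = 1%, 3%, 5%. The number lost is a fraction 1 − (1 − r)^k, where k is the count of later visits. The standard error contributed by that arm is multiplied by 1/√((1 − r)^k), taking subjects as equally informative. The starting numbers, 137 and 684, are the planned evaluable numbers.

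*All later visits count* (sample codes also remove the subject): k = 4 after Day 31 (Visits 3, 4, 5, 6) and k = 2 after Day 91 (Visits 5, 6).

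| r | ACWY loss | ACWY left | SE × | 0,2-months loss | left | SE × |
|---|---|---|---|---|---|---|
| 1% | 3.9% | 131.6 | 1.020 | 2.0% | 670.4 | 1.010 |
| 3% | 11.5% | 121.3 | 1.063 | 5.9% | 643.6 | 1.031 |
| 5% | 18.5% | 111.6 | 1.108 | 9.8% | 617.3 | 1.053 |

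*Only vaccination visits count* (sample codes act on their own visit): k = 2 after Day 31 (Visits 3, 5) and k = 1 after Day 91 (Visit 5). The ACWY loss is 1 − 0.99² = 2.0%, 1 − 0.97² = 5.9% and 1 − 0.95² = 9.8%. The Day 91 loss is 1%, 3% and 5%.

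With a PPS cut off at the analysed sample, these losses are zero.

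**The case against.** The strongest objection concerns the sample codes. Code 2100 (no post-vaccination serology) lists Visits 2, 4 and 6. Section 3.1 says blood is drawn from everyone whatever the testing status, and Table 1 gives the ABCWY and MenB_0_6 groups no Day 91 endpoint. If a missing result at any listed visit removed the subject, a group not tested at Visit 4 would disappear entirely, which cannot be meant. A reader might infer from the row for code 2090 that a mistimed Day 211 draw removes an ACWY subject's Day 31 result, or that a mistimed Day 91 draw removes an ABCWY subject's Day 211 result. The table permits that reading but does not establish it. This part of the objection stands, and the sample codes are a matter of ambiguity only.

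The objection does not reach the vaccination-type codes, which list visits without a post-vaccination sample.

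Three further limits also stand. First, a reader might infer that every VE is affected. Per-strain VE (Section 5.4.1.2) and all responder-based analyses (Section 5.3.1.2 and those that refer to it) use the full analysis set (FAS) and are untouched. Second, the 25% in Section 3.3 is a dropout allowance. Treating part of it as recoverable by changing the PPS has no support in the documents. Third, no mechanism ties a late Day 61 or Day 181 visit to the Day 31 result in this observer-blind study, so neither a direction of bias nor a false success is shown.

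Finally, the July 2019 SAP was written for a three-group study of about 450 subjects with no Month 1 reading. It shows that the sponsor knew how to state such a cut-off, but it does not prove what was intended later.

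**Conclusion.** The point holds for the vaccination-type codes in Amendment 4. A Day 61 or Day 181 vaccination deviation removes a valid Day 31 ACWY result from overall test-based VE and, among subjects without previous ACWY vaccination, from 4-fold-rise non-inferiority. A Day 181 vaccination deviation removes a valid Day 91 result from the 0,2-months test-based VE. For the sample codes the table is ambiguous and needs a statement.

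The demonstrable harm is lost precision, together with a primary population defined partly by events after the outcome. The size is unknown because the documents give no late-deviation rate. Under the assumed 1–5% per later visit, about 4–19% of Day 31 controls and 2–10% of Day 91 MenB_0_2_6 subjects would be retained by a timepoint cut-off if the sample codes also remove subjects. If they do not, the figures are about 2–10% and 1–5%. All of this is conditional on Section 4 of Amendment 5 not already having changed the rule.

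**What to change.** Check Section 4 of Amendment 5. If it is unchanged, replace the single PPS by three sets and fill in the last column of Table 4 accordingly.

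- **Month 1:** vaccination-type codes at Visit 1; sample codes at Visit 2.
- **Month 3:** vaccination-type codes at Visits 1 and 3 (2080 at Visit 3); sample codes at Visit 4.
- **Month 7:** vaccination-type codes at Visits 1, 3 and 5 (2080 at Visits 3 and 5); sample codes at Visit 6.

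State that a subject is excluded only for deviations up to and including the sample analysed, and that codes 2090, 2100, 2120 and 2130 act only on that sample's visit. Name the set to be used for each arm in Sections 5.3.1.1, 5.3.1.5, 5.3.1.8 and 5.3.1.9.

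The cost is SAP wording and elimination flags by timepoint. The PPS number will differ by endpoint and must be reported that way. In a Day 211 versus Day 31 contrast the two arms will be screened over different periods, which follows from the design's own reading times. No new data are needed.
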